## **5.2 Definition of Analysis Populations**

The following analysis sets will be identified prior to database lock, see section 10.3 of the protocol. Please note, that the FAS definition is slightly different from the ITT population in the protocol.

Screening	All patients who were screened (i.e. given informed consent)
Safety Set (SS)	All patients who inhaled at least one dose of (complete or partial) study medication. Subjects will be analyzed as treated.
Full Analysis Set (FAS)	All patients in the safety set (SS) who have at least one post treatment assessment.
Per-Protocol Set (PPS)	All patients in the FAS without a major protocol deviation that may significantly impact data integrity or patient safety.

The FAS set will be the primary analysis set for all efficacy analyses and the PPS set will be used to demonstrate robustness of results for the efficacy

endpoints. All other analyses will be based on the patients from the safety set.

All protocol violations/deviations will be reviewed and classified as either 'minor' (unlikely to appreciably affect trial outcomes) or 'major' (likely to affect outcomes) and this classification will be utilised to define the study populations for analysis purposes.

The assessment of major violations will be performed before the study database is locked and will be documented in the corresponding meeting/TC minutes. At a minimum the investigator, a sponsor representative and the CRA/monitor will participate in this review and will sign the meeting minutes.

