	
To be evaluated on the full cohort, and separately in the sub-cohort of those who test positive for SARS-CoV-2:
 

• Safety and tolerability of RESP301 in terms of:

○ % of participants able to tolerate the test dose in Parts 1(a), 1 (b) and 2

○ Total counts and cumulative incidence of:

▪ Adverse Events (AEs)

▪ Serious Adverse Events (SAEs)

▪ Suspected Unexpected Serious Adverse Reactions (SUSARs)

▪ Severe AEs

▪ Treatment-related AEs/SAEs

• Feasibility in terms of percentage of patients who, having experienced and correctly reported an exacerbation, receive the treatment within 48 hours of reporting their exacerbation

• Efficacy of RESP301 in terms of:

○ % of participants recovered by Day 7 and Day 14 post starting treatment

○ time to recovery (days until patient feels all their symptoms are back to their usual baseline (all VAS = 0))

○ preventing exacerbation-related hospitalisation and/or death

○ change in CCQ score

Duration of participation in the study	The overall study duration for each participant will be at most approximately 60 weeks, including one or more visits at a study centre in Parts 1/2, monthly follow-up calls, and, for those who experience an exacerbation, one week of treatment and additional monitoring calls at the beginning, during and following the treatment period.
Study population	Participants will be adult patients with spirometry-confirmed COPD or computerised tomography (CT) proven bronchiectasis, recruited from secondary and primary care sites in the UK.
Sample size	
Part 1(a):
 
We aim to recruit up to 48 participants. All participants who complete Part 1a, will also be eligible to enter Part 2 of the trial.
 
Part 1(b):
 
We aim to recruit 8 participants who are not experiencing an exacerbation. These participants will receive a short acting

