# **3. EFFICACY AND SAFETY VARIABLES**

## **3.1 Efficacy**

The primary objective in part 1 (Dose Finding Phase) is to determine the maximum tolerable dose (MTD) and the recommended therapeutic dose (RTD) of the single agent RESP301. For these decisions individual and cohort stopping criteria were defined, see section 7.7.2 and 7.7.3 of the protocol. In a Safety Advisory Committee (SAC) meeting prior to part 2 of this study these doses will be determined. Hence no single primary and/or secondary endpoint for part 1 was defined.

In part 2 (Expansion Phase), the primary endpoints are:

- Percentage of patients entering the dormant period who, having experienced and correctly reported an exacerbation, commence self-administration of the treatment at home on the day the treatment is delivered.
- Percentage of patients who, having experienced and correctly reported an exacerbation, receive the treatment within 48 hours of reporting their exacerbation.
- Compliance with RESP301 administration schedule over the treatment period: for those participants commencing treatment, the percentage of total doses taken.

The secondary endpoints, which will be analyzed by treatment dose and separately in the sub-group of patients who had a positive test result for SARS-CoV-2 are defined as:

- % of participants able to tolerate the test dose in Part 1(a), Part 1(b) and Part 2, i.e. able to complete the test dose without any of the following:
  - o Troublesome cough, chest pain or tightness, bronchospasm or dyspnea that is deemed unacceptable by the patient.
  - o methemoglobin >5% during or >3% post dose (30 or 60 mins)
  - o any treatment-related AE that led to participant not being able to complete the test dose, and/or be suitable to be enrolled into the dormant period in the Investigator's opinion
  - o for the first 50 patients who will undergo pre and post-test dose spirometry, >20% reduction in FEV1 from pre-test dose to post

---

test at 60 min dose with symptoms listed above (patients with >20% reduction in FEV1 without symptoms would be offered the option to continue in the study).

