## **5. METHODS OF ANALYSIS AND PRESENTATION**

### **5.1 General Principles**

The statistical analysis will be performed using the validated software package SAS version 9.4 or higher (SAS Institute Inc., Cary, NC 27513, USA).

All recorded and derived variables will be presented by treatment group and visits (if appropriate) using descriptive summary tables (continuous data: sample size, mean, standard deviation (SD), minimum, median, maximum; categorical data: sample size, absolute and relative frequency).

The mean and median will be presented to one more decimal place than the raw data. The SD will be presented to two more decimal places than the raw data. The percentages will be presented to 1 decimal place. In all the summaries, the treatment groups will be displayed in the following order: part 1 (RESP301 1 ml, 2 ml, ...6 ml, RESP+Vent 6 ml) and then part 2.

For all parameters, baseline is defined as the last available pre-treatment value (i.e. the last non-missing value available before study drug administration. In general, missing data will be treated as missing and no attempts will be made to impute values for missing data.

No formal interim efficacy analyses are planned in this study; however, several safety interim analyses by the Safety Advisory Committee (SAC) will be performed as detailed in the protocol, see section 7.7 for part 1 and an Independent Data Monitoring Committee (IDMC) will review the safety data on an ongoing basis as described in the DMC charter, see section 10.6 of the protocol.

Subjects who did not receive any study medication (screening failures) will be listed separately and not presented in any table or figure, except in the patient's disposition table.

The versions of the following international dictionaries (MedDRA version 26.1 and WHO DD, version 2024) will be used for medical coding:

Adverse events: Medical Dictionary for Regulatory Activities (MedDRA).

Medical Histories: Medical Dictionary for Regulatory Activities (MedDRA).

Medications: World Health Organization (WHO) Drug Dictionary including Anatomical Therapeutic and Chemical (ATC) classification.

If a medication in the drug dictionary (DD) table is associated with more than one ATC code, the first ATC code will be assigned to that medication.

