## **5.10 Analysis of Efficacy Variables**

All primary and secondary efficacy parameters, see section 3, will be summarized descriptively and no formal statistical analyses will be performed. The analyses will be performed by treatment group and overall, for both the FAS and PPS set using appropriate descriptive statistics. The results of the spirometry will also be presented over time, i.e. baseline, 30-, 60- and 90-minutes post baseline.

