## 15.2 Efficacy Results

Table 1.1	Summary of primary endpoints, part 2 – FAS/PPS set
Table 1.2	Summary of secondary endpoints – FAS/PPS set
Table 1.3	Summary statistics of spirometry over time – FAS/PPS set
Table 1.4	Summary of VAS scales – FAS/PPS set
Table 1.5	Summary statistics of explorative/sub-group analyses, if any – FAS/PPS set

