### **Appendix 16.2.6 Efficacy Data**

Listing 1	Primary endpoint, part 2 – Safety set
Listing 2	Secondary endpoints – Safety set
Listing 3	Spirometry – Safety set
Listing 4	VAS scales – Safety set

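### Same-day start and 48-hour receipt are defined over all correct reporters but analysed only in dosed participants; if the test dose is waived, undosed non-starters leave the denominator

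*SAP*

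**What the plan says.** **Endpoints.** SAP 3.1 lists three primary endpoints for Part 2.
- Same-day start: "Percentage of patients entering the dormant period who, having experienced and correctly reported an exacerbation, commence self-administration of the treatment at home", on the day of delivery. The protocol synopsis also makes this primary.
- Receipt of treatment within 48 hours of the report, again among those who experienced and correctly reported an exacerbation. In the protocol synopsis this is a secondary endpoint with the same denominator: "Feasibility in terms of percentage of patients who, having experienced and correctly reported an exacerbation".
- Compliance, which alone is limited to participants who begin treatment.

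**Analysis sets.** SAP 5.2 defines the Safety Set as "All patients who inhaled at least one dose of (complete or partial) study medication. Subjects will be analyzed as treated" and the FAS as "All patients in the safety set (SS) who have at least one post treatment assessment". The Per-Protocol Set lies inside the FAS. SAP 5.2 remarks that the FAS differs slightly from the protocol's ITT population but gives no consequence. The ITT in Protocol Table 10-1 is everyone enrolled into the treatment period, with no condition on inhaling a dose.

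**Outputs.** SAP 5.10 says of all primary and secondary efficacy parameters: "The analyses will be performed by treatment group and overall, for both the FAS and PPS set". The planned table in SAP 15.2 is "Summary of primary endpoints, part 2 – FAS/PPS set", and the listing in Appendix 16.2.6 is "Primary endpoint, part 2 – Safety set". SAP 5.1 adds: "Subjects who did not receive any study medication (screening failures) will be listed separately and not presented in any table or figure", with the disposition table as the only exception.

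**Test dose.** SAP 2.2 and SAP 4 give a test dose to the first 50 Part 2 participants. The committee may then let the remainder enter the dormant period without one.

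**The concern.** The endpoint definitions count people who reported an exacerbation, whether or not they went on to inhale anything. The analysis sets count only people who inhaled something. The two agree as long as everyone has had a test dose. Once the test dose is waived, a participant can enter the dormant period, correctly report an exacerbation, never start treatment, and never have been dosed. That person is a failure for same-day start but is outside the Safety Set, the FAS and the Per-Protocol Set. A test-dosed participant who behaves in the same way stays in, so whether a failure counts would depend on test-dose status.

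Treating these patients in the community is a primary objective, and same-day start is its direct measure. Non-starting is foreseeable: the protocol synopsis sends a pack only to participants who are eligible and still willing at the remote visit. SAP 4 assumes that those who exacerbate will begin treatment. An analysis set that removes non-starters would partly build that assumption into the result. No planned table or listing gives these two endpoints with undosed reporters in the denominator.

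**Working it through.** **Inputs from the documents**
- 150 participants enrolled and 30 expected to exacerbate (SAP 4). This is 30/150 = 20%, given as an estimate; no formal sample size calculation was done.
- 50 test-dosed if the waiver is granted, leaving up to 100 of 150 without a test dose (SAP 2.2 and 4).

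**Assumptions, not in the documents**
- All 30 who exacerbate report correctly, and they split in proportion to test-dose status: 30 × 100/150 = 20 undosed and 10 dosed. None of the 20 was dosed in Part 1; each who was would reduce the 20.
- Every dosed reporter has a post-dose assessment and so is in the FAS.
- A never-start rate *f*, equal in dosed and undosed reporters.
- A share *s* of starters who start on the delivery day.

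**Same-day start**

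All reporters: 30·s·(1 − f)/30 = s(1 − f). FAS: 30·s·(1 − f)/(30 − 20f).

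| f | All reporters (s = 1) | FAS (s = 1) | Difference, s = 1 | Difference, s = 0.7 |
|---|---|---|---|---|
| 0% | 30/30 = 100% | 30/30 = 100% | 0 | 0 |
| 5% | 28.5/30 = 95.0% | 28.5/29 = 98.3% | +3.3 | +2.3 |
| 10% | 27/30 = 90.0% | 27/28 = 96.4% | +6.4 | +4.5 |
| 20% | 24/30 = 80.0% | 24/26 = 92.3% | +12.3 | +8.6 |

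In whole patients, one undosed never-starter gives 29/29 = 100% instead of 29/30 = 96.7%, or +3.3 points. If all 150 are test-dosed, the FAS denominator stays at 30 and the difference is zero for every *f*.

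**Direction for same-day start.** Each excluded person adds nothing to the numerator and one to the all-reporter denominator, so this exclusion cannot lower the percentage.

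**48-hour receipt.** Take 6 never-starters (2 dosed, 4 undosed) and 24 starters, of whom 21 receive the pack on time.
- None of the 6 received it on time: 21/30 = 70.0% against 21/26 = 80.8% in the FAS (+10.8).
- All 6 received it on time: 27/30 = 90.0% against 23/26 = 88.5% in the FAS (−1.5).

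The direction therefore depends on whether the excluded people had the pack in time.

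**Compliance.** Its denominator is starters, who have all inhaled a dose, so the inhaled-dose condition does not affect it.

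**The three candidate denominators.** With 6 non-starters, 4 of them undosed, suppose 2 of the 6 declined or were ineligible at the remote visit. All reporters give 24/30 = 80.0%, the protocol ITT gives 24/28 = 85.7% and the FAS gives 24/26 = 92.3%.

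**The case against.** **The effect is doubly conditional.** It needs a waiver and at least one undosed reporter who never starts. In the protocol 50 is a minimum, continued test dosing is an explicit option, and the documents do not show whether a waiver was granted. The only start rate they imply is that everyone who exacerbates begins treatment, which gives no bias. All of this stands. It limits the size but does not remove the conflict in the text.

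**The net error in the FAS need not be upward.** The FAS also requires a post-treatment assessment. Losing a same-day starter for want of one would lower the percentage. This stands too; the upward direction belongs to the exclusion of undosed non-starters alone.

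**The SAP discloses that the FAS differs from the ITT.** It does, but it does not say that the difference changes a feasibility denominator.

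**A programmer would use the endpoint's own denominator.** The table title and SAP 5.10 fix the FAS and Per-Protocol Set, and SAP 5.1 keeps undosed subjects out of the table. One might read SAP 5.1 as meaning only true screen failures, which Protocol 6.5 defines by eligibility. Even so, SAP 5.2 still excludes the undosed.

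**Someone with no delivery may be not evaluable rather than a failure.** The endpoint refers to the delivery day, and packs go only to willing participants. The visible text does not settle this, and Protocol 10.4.2 is partly redacted. That is a fair reason to show the protocol ITT percentage beside the all-reporter one.

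**A stronger reading that a reader might infer.** One could take the post-treatment assessment in the FAS definition to mean an assessment after home treatment, so that every non-starter drops out even without a waiver. The SAP does not support this. It reports test-dose tolerability for Parts 1(a), 1(b) and 2, and spirometry over time, in the FAS and Per-Protocol Set by treatment group. The Part 1 groups receive only single supervised doses, so an assessment after such a dose must qualify.

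**Conclusion.** The conflict holds, in a conditional form. SAP 3.1 sets the denominator as correct reporters, while SAP 5.1, 5.2, 5.10 and Table 1.1 of SAP 15.2 restrict it to the dosed. If the test dose is waived, undosed never-starters leave a primary feasibility endpoint, and for same-day start that can only flatter the result. For 48-hour receipt the direction is open.

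The inflation runs from nothing, if all undosed reporters start, through 3.3 points for a single undosed never-starter, to about 12.3 points at a 20% never-start rate. These figures rest on the assumptions listed above, and the never-start rate has no source in the documents. Confidence is high on the textual conflict and low on the size. No test, threshold or go/no-go rule uses the percentage, so the harm is a descriptive figure that looks better than what happened. It should be fixed, but it does not threaten the trial.

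**What to change.** 1. Analyse same-day start and 48-hour receipt in all dormant-period participants who correctly report an exacerbation, regardless of any inhaled dose. Do this in Table 1.1 of SAP 15.2 and Listing 1 of Appendix 16.2.6, under the Part 2 group.
2. Count never-starters as failures for same-day start, and non-receipt within 48 hours as failure for receipt.
3. Report how many reporters declined or were found ineligible at the remote visit, and give both percentages in the protocol ITT beside the main figure.
4. Keep the starters-only denominator for compliance.
5. Limit the SAP 5.1 exclusion to screen failures as Protocol 6.5 defines them, so that enrolled but undosed Part 2 participants can appear in these tables.

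The cost is SAP wording and one analysis-set flag; no new data collection is apparent. The downside is that the reported percentages may be lower, in part because decliners and ineligible reporters count as failures in the main figure. Item 3 lets the reader see how much of the shortfall they explain.

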### **5.3 Disposition of Subjects**

A summary of the subject disposition will be created including number of patients screened, number of screen failures, if any, number of patients treated, number of patients who completed the study in each treatment group. In addition, a summary of the number and percentage of patients in the safety set who were available at each visit will be presented by treatment group and overall.

### **5.4 Demographic and Baseline Characteristics**

Demographic characteristics (age, gender and ethnicity) and body measurements (height, weight and BMI) and vital signs (body temperature, systolic blood pressure, diastolic blood pressure, heart rate and respiratory rate) collected at baseline will be summarized by treatment group and overall, for the safety set.

Body mass index (BMI in kg/m\*\*2) will be calculated as weight (in kg) divided by height (in m) \*\*2.

Any additional baseline characteristics, like smoking status, COPD and bronchiectasis history will also be presented descriptively by treatment group and overall.

### **5.5 Medical History**

Medical history and concurrent diseases will be coded using MedDRA. The number and percentage of patients with past medical conditions grouped by MedDRA SOC will be displayed on the preferred term level (PT) by treatment group for the safety set. A similar summary will be produced for concurrent medical conditions at baseline (before start of first administration of study medication).

### **5.6 Physical Examination**

The number and percentage of patients with abnormal physical examination at baseline will be displayed for each body system as indicated in the eCRF in the safety set.

All the details collected in the eCRF of the physical examination at baseline will be presented in a separate listing for all subjects in the safety set.

## **5.7 Protocol Deviations**

Any protocol deviations (minor and major) will be identified by the clinical team prior to locking the database. The number and percentage of patients with each deviation and each treatment group will be summarized for the safety set.

## **5.8 Prior and Concomitant Medications**

Prior and concomitant medications will be coded using WHO-DD and will be assigned to the first corresponding ATC code. All the medications will be listed for the safety set.

The number and percentage of subjects with concomitant medications ongoing at baseline (i.e. ongoing the day before administration of first dose of study medication) classified by ATC levels 2 and 3 will be displayed by treatment group in the safety set. A similar summary will be produced for concomitant medication started after baseline (i.e. those medications started on or after the day of first dose and on or before the date of last dose). Any medications starting after last dose will be listed only.

## **5.9 Extent of Exposure**

Overall compliance regarding the administration of the study medication during the study part 2 will be calculated for the dormant phase based on the number of dispensed medications minus the number of medications returned as a percentage of the number of medications that should have been administrated. A summary with descriptive statistics will be produced by treatment group in the safety set. For part 1 and the test dose phase in part 2 the number and percentage of correct administrations will be presented.

The exposure to study medication will be calculated in days as:

Last dose date of study medication – First dose date + 1.

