100295

100296

100297

100298

100299

100300

100301

100302

100303

100304

100305

100306

100307

100308

100309

100310

100311

100312

100313

100314

100315

100316

100317

100318

100319

100320

100321

100322

100323

100324

100325

100326

100327

100328

100329

100330

100331

100332

100333

100334

100335

100336

100337

100338

100339

100340

100341

100342

100343

100344

100345

100346

100347

100348

100349

100350

100351

100352

100353

100354

100355

100356

100357

100358

100359

100360

100361

100362

100363

100364

100365

100366

100367

100368

100369

100370

100371

100372

100373

100374

100375

100376

100377

100378

100379

100380

100381

100382

100383

100384

100385

100386

100387

100388

100389

100390

100391

100392

100393

100394

100395

100396

100397

100398

100399

100400

100401

100402

100403

100404

100405

100406

100407

100408

100409

100410

100411

100412

100413

100414

100415

100416

In Part 1, participants who do not meet any of the Individual Stopping Criteria (Section 7.7.2), and are suitable in the Investigator's opinion to proceed, can proceed to the next cohort (subject to SAC review).

In Part 2, participants who satisfactorily tolerate the test dose based on the above assessments, and are suitable in the Investigator's opinion to proceed, will be enrolled into the dormant period of the study.

[figure not shown]
Participants who completed the Screening visit and test dose but were not suitable to continue to the dormant period, should be followed up with a phone call 7 [REDACTED]

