## 2.2 Study Design

This is a phase II, single-group, non-randomized, two-center, open-label study conducted in two parts.

In part 1 (Dose Finding Phase), eligible patients will be administered a single dose of RESP301 under clinical supervision. The first eight patients (group 1) will receive a dose of 1 ml, the next eight patients (group 2) 2 ml, the next eight patients (group 3) 3 ml, etc. until a maximum dose of 6 ml. After the completion of each dose level (treatment group) the safety data will be reviewed by the PIs and Sponsor before proceeding to the next higher dose. After the completion of all groups a safety advisory committee (SAC) will review the data from all participants and determine a Maximum Tolerated Dose(MTD) and a Recommended Therapeutic Dose (RTD).

Thereafter eight eligible patients will be administered a single dose of RESP301 at the MTD in combination with a short acting bronchodilator also under clinical supervision.

In part 2 (Expansion Phase), a minimum of 150 patients will be enrolled into the Expansion Phase and treated at the Recommended Therapeutic Dose (RTD) determined in Part 1. The expansion phase is split into three periods, a baseline visit, a dormant period (max. 12 months) and a treatment period (7 days). The first 50 patients at baseline will receive a RTD test dose on site to further investigate the safety and tolerability of RESP301.

An Independent Data Monitoring Committee (IDMC) will review this data and decide whether further RTD test doses should be administered to further patients before enrolling them into the Dormant Period or whether patients could be enrolled into the dormant period without a RTD test dose at baseline.

Female of non-childbearing potential or male  $\geq 35$  years of age, at the time of signing the informed consent with spirometry-confirmed COPD or computerized tomography (CT) proven bronchiectasis are included in the study. Further details of the inclusion/exclusion criteria are defined in sections 6.2 and 6.3 of the protocol.

Eligible patients in part 1 may be enrolled in more than one of the seven treatment groups and patients from part 1 will also be eligible to enter Part 2 of the trial.

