**Table 3: Schedule of Study Assessments (Part 2)**

Procedure	Screen 1	Screen 2/ Baseline Visit 	Dormant Period (monthly calls)	Pre-Treatment call (within 24-72 hrs of exacerbation onset)	Treatment Period (daily monitoring calls for 8 days)	Post Treatment Follow-up call (Day $14\pm 3$ PEoT)	Post Treatment Follow-up call (Day $28\pm 3$ PEoT)	Early withdrawal (Days 0, 14 or 28 $\pm$ 3)
Informed Consent	X	X						
Inclusion and Exclusion Criteria	X	X						
Demographics	X							
Medical History	X			X	X	X	X	X
Medication history and concomitant medications	X	X		X	X	X	X	X
Height, Weight and BMI	X							
Physical Examination 	X	X						
Pulmonary function test 	X	X						
Vital signs	X	X						
Methemoglobin level	X	X						
RESP301 administration 		X			X			
CCQ		X	X		X 	X		
Instructions of nebulizer		X		X	X			
Follow-up 			X					
Review of symptoms				X	X	X		
AE/SAE review	X	X			X	X	X	X
VAS 					X	X		

Body temperature 				X	X	X		
Treatment compliance					X			

 Patients who received a RTD test dose only and did not proceed to the dormant period, will receive a follow-up call on day 7±3 to discuss and record AEs.

 Only done if deemed necessary by the investigator

 Only done in patients who received a RTD test dose at the Baseline visit

 At baseline a single RTD dose for patients who were assigned to test dose and at the treatment period TID for 1- 7 days in patient with an exacerbation

 Done at Day 1 and Day 7

 Patients reminded to contact the study team if they experience exacerbation symptoms

 Daily during the treatment period, and if not recovered by end of treatment, continued until recovery or Day 14 post end of treatment

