## **4. SAMPLE SIZE JUSTIFICATION**

The primary objective of this study is to determine the MTD and RTD of RESP301 and to assess feasibility. No formal sample size calculation was performed. In Part 1, we aim to recruit up to 56 participants (8 per dose group) to receive one dose of RESP301 (alone or in combination).

In Part 2, we aim to recruit around 150 patients from secondary care and primary care sites in the UK into the dormant period. The first 50 consented participants will receive an initial test dose of RESP301 before progressing to the dormant period. If, based on the first 50 participants, the DMC determines that it is safe to do so, the remaining consenting participants will not be required to receive a test dose before progressing to the dormant period. It is estimated that over 12 months, 30 of the 150 enrolled participants will exacerbate. These participants will commence self-administered RESP301 treatment. Non-exacerbating participants will receive no further study interventions.

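### SAP 5.9 ties Part 2 compliance to a phase without dosing and measures it by unreturned drug, and its exposure formula counts the drug-free gap between test dose and treatment course

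*SAP*

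**What the plan says.** SAP 5.9 gives three rules.

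- **Part 2 compliance** "will be calculated for the dormant phase based on the number of dispensed medications minus the number of medications returned". It is expressed as a percentage of the doses that were due and summarised in the safety set.
- **Test doses** are handled apart: "For part 1 and the test dose phase in part 2 the number and percentage of correct administrations will be presented".
- **Exposure** in days is "Last dose date of study medication – First dose date + 1". The formula names no part, phase or treatment group.

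The dosing schedule is in SAP Table 3, footnote 4: "At baseline a single RTD dose for patients who were assigned to test dose and at the treatment period TID for 1- 7 days". The same table marks treatment compliance in the treatment period column only.

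SAP 3.1 makes compliance over the treatment period a Part 2 primary endpoint, defined as "for those participants commencing treatment, the percentage of total doses taken".

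The two compliance results go to different tables. The SAP 5.9 figure goes to section 15.1, Table 5.1 (safety set). The primary endpoints go to section 15.2, Table 1.1 (FAS and PPS). SAP Table 1 has one group for all Part 2 dosing, group 8, so test dose and home course are not separated.

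**The concern.** Three things do not fit.

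1. The compliance rule names a phase in which nothing is administered, so as written it has no denominator.
2. The rule counts drug that did not come back, whereas the endpoint counts doses taken. For self-administered home treatment these can differ, and nothing in SAP 5.9 tells the reader that its figure is a different quantity. The report could show two compliance percentages for the same patients without saying why they differ.
3. A patient who has a test dose at baseline and a course months later has a first and a last dose date on either side of the dormant period. The exposure formula treats every day between them as exposed.

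At stake is whether the descriptive exposure and compliance figures mean what their labels say. No hypothesis test depends on them.

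**Working it through.** The plan states no compliance or exposure result that could be reproduced. The only planning figure needed is in SAP section 4: "It is estimated that over 12 months, 30 of the 150 enrolled participants will exacerbate", that is 30/150 = 20%.

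**Step 1: the phase.** The Protocol synopsis schedules three doses a day for 7 days, so 3 × 7 = 21 doses are due in the treatment period. In the dormant period 0 doses are due, so a percentage of doses due is undefined. The phrase cannot stand for the test dose, because SAP 5.9 covers that in its own sentence. The treatment period is the only reading left.

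**Step 2: the compliance measure.** Let D be doses dispensed, R returned, T taken and S due.

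- SAP 5.9: 100 × (D − R)/S
- SAP 3.1: 100 × T/S, if S is also taken as its denominator (SAP 3.1 does not state one)

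With D = S = 21 (an assumption), the difference is 100 × (untaken and unreturned doses)/21. Each such dose adds 1/21 = 4.8 percentage points. For a patient who takes 15 of 21:

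| Untaken doses returned | SAP 5.9 | Doses taken |
|---|---|---|
| 6 | 15/21 = 71.4% | 71.4% |
| 3 | 18/21 = 85.7% | 71.4% |
| 0 | 21/21 = 100% | 71.4% |

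Under this assumption the two agree only when every untaken dose is returned; otherwise SAP 5.9 is higher. The populations differ too. The safety set includes test-dosed patients who never start a course and so have no course doses due. At 50 test-dosed and 20% treated, that is 50 − 10 = 40 patients.

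**Step 3: exposure.** Protocol 5.1 places the baseline visit, with any test dose, on Day 0. If a 7-day course starts on day t, the last dose falls on day t + 6.

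- SAP formula: (t + 6) − 0 + 1 = t + 7 days
- Days with a dose: 1 + 7 = 8

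| t (assumed) | SAP formula | Dosing days |
|---|---|---|
| 28 | 35 | 8 |
| 182 | 189 | 8 |
| 364 | 371 | 8 |

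The Protocol synopsis allows the course to run into Day 8. The formula then gives t + 8 against 9 dosing days. A treated patient without a test dose gets 7 days (or 8), which is correct.

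**Step 4: how many patients.** Assume the same 20% for test-dosed and other patients.

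- 50 test-dosed, all entering the dormant period: 50 × 0.20 = 10 of 30 treated (33%).
- Not all will enter, since Protocol 8.1.6 provides for "Participants who completed the Screening visit and test dose but were not suitable to continue to the dormant period". If 80% enter (an assumption): 0.8 × 50 × 0.20 = 8 of 30 (27%).
- All 150 test-dosed: 150 × 0.20 = 30 of 30.

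As an illustration of the mean, take 10 affected patients with t = 180 and 20 without a test dose. The formula gives (10 × 187 + 20 × 7)/30 = 67.0 days. Actual dosing days average (10 × 8 + 20 × 7)/30 = 7.3.

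**Step 5: where the figures go.** SAP sections 15.1 to 15.3 list no exposure table, so exposure would appear only through the general rule in SAP 5.1 that derived variables are summarised by treatment group. The adverse event summaries in SAP 5.11 are counts and percentages of patients, without person-time. SAP 5.8 uses the same first-to-last-dose window for medications started after baseline (section 15.1, Table 3.4). That window also spans the gap in test-dosed patients.

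**The case against.** The strongest reply is that little here would mislead a competent analyst. The phase is an obvious slip, since nobody can calculate compliance where no dose is due. Drug accountability beside a doses-taken endpoint is ordinary practice, in a different table and population, and the SAP allows clarifying footnotes at programming. The return rules may lie in redacted protocol text (7.2.3, 7.4, 8.4). Exposure has no listed table.

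Most of this stands, and it limits the point. It does not repair the exposure formula. The separate test-dose sentence concerns correct administrations, not exposure, and presentation by treatment group does not help when test dose and course share group 8. Nor does SAP 5.9 call its figure accountability; it presents it as compliance with administration.

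A reader might infer more than the documents support:

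- **That the primary endpoint is in doubt.** It is not: SAP 3.1 fixes which result is the endpoint. A second table of dispensed minus returned is not in itself an error.
- **That SAP 5.9 contradicts a denominator in SAP 3.1.** SAP 3.1 states none. Footnote 4 of SAP Table 3, with its range of 1 to 7 days, leaves open what counts as due after early stopping.
- **That Part 1 dates inflate Part 2 exposure**, because "patients from part 1 will also be eligible to enter Part 2 of the trial". SAP Table 1 keeps Part 1 in its own groups and SAP 5.1 presents by group, which largely removes this.
- **That adverse event rates are distorted.** None uses exposure time.

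**Conclusion.** The point holds for two descriptive rules in SAP 5.9.

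- **Compliance.** The phase is wrong as written, evidently by a slip. The measure departs from the SAP 3.1 endpoint by 4.8 points for each untaken, unreturned dose, assuming 21 dispensed and 21 due. The documents visible here give no return rate, so the size in the trial is unknown and the worked percentages are illustrations.
- **Exposure.** The formula is wrong for Part 2 patients who have both a test dose and a course: t + 7 days instead of 8. The expected number is about 10 of 30 treated if 50 are test-dosed, somewhat fewer if some do not enter the dormant period, and up to 30 if all are test-dosed. This rests on the SAP's 30 in 150 applying equally to both kinds of patient; the values of t are assumed.

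The consequence is confined to descriptive output. The SAP 5.8 medication window is a secondary matter. Correction before database lock is worthwhile because the rules are plainly not what is meant and the repair is small.

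**What to change.** In SAP 5.9:

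1. Replace *dormant phase* by *treatment period*, and restrict the summary to participants who commence treatment.
2. Refer to the SAP 3.1 endpoint for doses taken, and state its denominator. Doses scheduled for the course is a proposed choice, since SAP 3.1 leaves it open.
3. Keep dispensed minus returned, labelled as drug accountability.
4. Calculate exposure separately for the test dose and for the treatment course, as dosing days and number of doses, using dates within each part.

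Optionally, note in SAP 5.8 that the window for Table 3.4 of section 15.1 spans the dormant gap in test-dosed patients, and show medications started in that gap separately so that they are not lost.

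The cost is a few sentences in SAP 5.9, and one or two in SAP 5.8 if the option is taken. No new data are needed: the SAP formula already relies on dose dates, and Protocol 5.1 provides for a daily dose diary and daily compliance calls.
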